AUTONOMOUS UNIVERSITY “BENITO JUÁREZ” OF OAXACA (UABJO)

STUDY PROTOCOL:

EFFECT OF VITAMIN D SUPPLEMENTATION ON STRENGTH AND MUSCLE GAIN IN OLDER ADULTS WITH OBESITY

NCT: Pending
Document versión: Version 1.0

Principal investigator:
[name]
[contact]
[name]
UABJO

Study Site: Instituto Mexicano del Seguro Social (IMSS)
Family Medicine Unit 24
Miahuatlán de Porfirio Diaz, Oaxaca, Mexico

JUNE 2023

STUDY PROTOCOL

Title: Effect of Vitamin D Supplementation on Muscle Strength and Muscle Mass in Older Adults With Obesity in Miahuatlán de Porfirio Díaz, Mexico (2023–2024)

Principal Investigator: M.N.C. [name] Doctoral Program in Biosciences, Faculty of Medicine, UABJO Email: [contact] [contact]

Study Site: Mexican Social Security Institute (IMSS) Family Medicine Unit No. 24 (UMF 24) Miahuatlán de Porfirio Díaz, Oaxaca, Mexico

Study Design: Randomized, placebo-controlled, parallel-group clinical trial; single-blind (participants).

Study Dates: Start: November 2023 End of follow-up/data lock: April 2024

Background and Rationale: Obesity in older adults is a growing public health concern in Mexico. The coexistence of excess body fat with reduced muscle mass and strength—known as sarcopenic obesity—is associated with frailty, impaired mobility, increased risk of falls, and decreased quality of life. Vitamin D plays an important role in muscle physiology, influencing protein synthesis, mitochondrial function, and neuromuscular coordination. Older adults often have low serum vitamin D levels due to decreased skin synthesis, limited sunlight exposure, and dietary insufficiency. Although randomized trials have evaluated vitamin D supplementation for muscle function, results remain inconsistent, and evidence in Mexican older adults with obesity is limited. This trial evaluates whether high-dose vitamin D improves muscle strength and muscle mass in this population.

Research Question: What is the effect of daily supplementation with 10,000 IU of vitamin D3 for 12 weeks on muscle strength and muscle mass in older adults with obesity receiving care at IMSS UMF No. 24?

Objectives: Primary objective: To evaluate the effect of daily vitamin D3 10,000 IU for 12 weeks on muscle strength and muscle mass in older adults with obesity.

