Secondary objectives: 1) To compare changes in body fat percentage, body adiposity index (BAI), abdominal volume index (AVI), and visceral fat. 2) To assess changes in physical performance using the Short Physical Performance Battery (SPPB). 3) To analyze changes in serum 25-hydroxyvitamin D concentrations.

Study Design and Methods: Interventional clinical trial with two parallel arms. Participants are randomly assigned to a vitamin D group or placebo group. The intervention period is 12 weeks per participant.

Study population: Older adults (≥ 60 years) with $\text{BMI} \geq 30 \text{ kg/m}^2$ attending IMSS UMF No. 24.

Inclusion criteria: - Age ≥ 60 years. - $\text{BMI} \geq 30 \text{ kg/m}^2$. - Receiving care at IMSS UMF No. 24. - Ability to perform physical tests (handgrip, SPPB). - Ability and willingness to provide written informed consent. - Willingness to take one capsule daily for 12 weeks and attend all visits.

Exclusion criteria: - Hypercalcemia or major calcium metabolism disorders. - Current use of high-dose vitamin D supplements ($\geq 1,000$ IU/day). - Use of medications affecting vitamin D metabolism (e.g., anticonvulsants, systemic corticosteroids). - Severe renal or liver disease. - Active cancer or recent chemotherapy. - Major musculoskeletal or neurological impairment preventing testing. - Cognitive impairment limiting understanding or cooperation. - Participation in another clinical trial in the last 3 months. - Any condition considered unsafe by investigators.

Intervention: Vitamin D arm: 10,000 IU vitamin D3 (cholecalciferol) oral capsule once daily for 12 weeks. Placebo arm: visually identical placebo capsule once daily for 12 weeks. Participants are asked to maintain their usual diet and medical treatment.

Assessments: Baseline and week 12: - Anthropometry (weight, height, BMI, waist circumference). - Body composition by bioelectrical impedance (muscle mass, fat mass, visceral fat, metabolic age). - Handgrip strength using a handheld dynamometer. - SPPB score. - Serum 25-hydroxyvitamin D.

Sample Size: Planned sample size: 30 participants (approximately 15 per arm), taking into account expected effect size and 80% power. Final analyzed sample: 29 participants.

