Statistical Analysis: Normality will be assessed with the Shapiro–Wilk test. Between-group comparisons will be performed with Mann–Whitney U tests for continuous variables, and chi-square or Fisher's exact test for categorical variables. Within-group changes (baseline vs week 12) will be analyzed with Wilcoxon signed-rank tests. A p-value <0.05 will be considered statistically significant.

Ethics: The study follows the Declaration of Helsinki and applicable Mexican health research regulations. All participants provide written informed consent. Data are coded to preserve confidentiality. Risks are considered minimal and include mild discomfort from blood sampling and rare minor side effects of vitamin D. Participants may withdraw at any time without affecting their medical care.

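### Two unranked primary muscle outcomes share a per-test 0.05 threshold: if an effect on either may be declared, the false-positive rate is about 7–10%, and Holm would hold it below 5%

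*Protocol*

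**What the plan says.** Under Objectives, the protocol gives a single primary objective with two outcomes: "To evaluate the effect of daily vitamin D3 10,000 IU for 12 weeks on muscle strength and muscle mass in older adults with obesity". The Background and Rationale pairs them in the same way: "This trial evaluates whether high-dose vitamin D improves muscle strength and muscle mass in this population". Neither outcome is placed first.

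The Statistical Analysis section assigns one method to the comparison of arms, "Between-group comparisons will be performed with Mann–Whitney U tests for continuous variables", and another to change within each arm, "Within-group changes (baseline vs week 12) will be analyzed with Wilcoxon signed-rank tests". It then gives one threshold for everything: "A p-value <0.05 will be considered statistically significant". It has no split of the 5%, no testing order and no statement of how many outcomes must succeed.

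The Sample Size section gives one power figure: "Planned sample size: 30 participants (approximately 15 per arm), taking into account expected effect size and 80% power". It names neither the outcome nor the size of effect that this figure refers to.

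**The concern.** A threshold of 0.05 per test is the error rate of the primary conclusion only if that conclusion rests on one test, or on both tests together. With two unranked outcomes and no success rule, the protocol allows an effect to be announced on whichever outcome crosses 0.05. The chance of announcing something when nothing is there is then higher than the threshold suggests.

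The same threshold also covers the within-group tests of the muscle outcomes: two arms times two outcomes, so four tests. These do not compare vitamin D with placebo, yet nothing in the analysis text ranks them below the between-arm tests. With about 15 participants per arm, one nominally significant muscle result could easily become the headline, so it matters what that result is worth.

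**Working it through.** **Inputs.** From the protocol: two primary outcomes, the Mann–Whitney test between arms, a threshold of 0.05, and about 15 per arm (14 vs 15 if 29 are analysed). Assumed: two-sided tests (the protocol does not state sidedness), normally distributed data for the simulations, and a correlation between the two outcomes of 0, 0.5 or 0.8 (the protocol gives none).

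**The plan's own figure.** The 30 participants at 80% power cannot be reproduced, because no effect size or SD is given. Solving backwards with the normal approximation, the standardised difference is (1.960 + 0.842) × √(2/15) = 1.02. Simulation of the exact Mann–Whitney test gives 79.6% power at 1.10 SD and 80.7% at 1.12 SD. So 80% per outcome corresponds to about 1.1 SD. This value is used below only as a reference point for the cost of the fix. It is not the investigators' assumption.

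**Size of one test, 15 vs 15.**
- Exact test: reject if U ≤ 64; two-sided size 0.04533.
- Normal approximation without continuity correction: reject if U ≤ 65; size 0.05022.

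**Either outcome suffices, neither has an effect.** At correlation 0 the rate is 1 − (1 − size)²:
- exact: 1 − (1 − 0.04533)² = 0.0886
- uncorrected approximation: 1 − (1 − 0.05022)² = 0.0979
- uncorrected approximation, 14 vs 15 (size 0.05109): 1 − (1 − 0.05109)² = 0.0996

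The other correlations come from 400,000 simulated trials of 15 vs 15:

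| Correlation | Exact | Uncorrected approximation | Holm, exact |
|---|---|---|---|
| 0 | 8.9% | 9.8% | 4.6% |
| 0.5 | 8.3% | 9.2% | 4.5% |
| 0.8 | 7.3% | 8.1% | 3.9% |

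The first Holm entry can be checked by hand. The exact size at 0.025 is 0.02350, and 1 − (1 − 0.02350)² = 0.0464.

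Each column should be read against its own single-test size. For the exact test, 8.86/4.53 = 1.95 at correlation 0 and 7.34/4.53 = 1.62 at 0.8.

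**False claims of benefit only.** Half the exact two-sided size is 0.04533/2 = 0.0227. For two independent outcomes, 1 − (1 − 0.0227)² = 0.045. With positive correlation, significant results in opposite directions are rare, so halving the two-sided rate is accurate enough: 8.3%/2 = 4.2% at 0.5 and 7.3%/2 = 3.7% at 0.8. The range is 3.7–4.5%, against 2.3% for one test.

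**Both outcomes required.** The error rate cannot exceed the size of one test. If neither outcome has an effect, it is 0.2%, 0.7% and 1.7% at correlations 0, 0.5 and 0.8.

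**Power under Holm at 1.1 SD, exact test.**
- Effect in one outcome only: power for that outcome is 79.5% unadjusted and 70.5% with Holm.
- Effect in both, per outcome: this is half the sum of P(at least one) and P(both), so (91.2 + 62.4)/2 = 76.8%, (85.3 + 66.5)/2 = 75.9% and (80.2 + 70.2)/2 = 75.2% at correlations 0, 0.5 and 0.8.
- Effect in both, at least one significant: 95.8%, 91.5% and 87.4% unadjusted; 91.2%, 85.3% and 80.2% with Holm.

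**The case against.** The strongest reply is that a success rule or multiplicity rule often sits in the statistical analysis plan, which is not shown, so its absence here proves nothing. The quoted threshold is also a conventional per-test statement, and nowhere does the protocol present 0.05 as the error rate of a combined claim. That limits the point but does not remove it. The protocol itself fixes the two-part objective and the uniform threshold, and between them they permit a claim on either outcome at 0.05. A better rule can be set against the stated one. If a dated plan already contains such a rule, the protocol need only adopt it.

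The second reply is that the objective, research question and rationale all join the outcomes with "and", so requiring both is at least as natural a reading. This stands in full. No passage says that one outcome is enough, and if both are required the per-test 0.05 inflates nothing.

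Three stronger readings are tempting and are not supported:

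- A reader might take 7–10% as the chance of falsely claiming that vitamin D helps. That figure also counts results favouring placebo; the false-benefit rate is about half of it.
- A reader might conclude that the 80% power is wrong. If both outcomes were required and 80% applied to each, joint power would be 64–73% for correlation 0 to 0.8. But the protocol does not say whether the 80% is per outcome or joint, so no error is shown.
- A reader might infer from "Final analyzed sample: 29 participants", in a Version 1.0 dated June 2023, before the November 2023 start, that the analysis rule was chosen after the data were seen. The sentence shows that the document's date and content disagree. It does not show when the analysis text was written, and it changes none of the figures here. It is a separate dating matter.

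**Conclusion.** The concern holds in conditional form. If an effect may be declared on either muscle outcome, the protocol's rule carries a two-sided false-positive rate of about 7–10%. That is some 1.6 to 1.95 times the rate of a single test, and false claims of benefit rise from about 2.3% to 3.7–4.5%. If both outcomes must succeed, the error rate is not inflated. The protocol's wording does not decide between the two.

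The figures rest on two-sided tests, two between-arm comparisons, normal data and an assumed correlation between 0 and 0.8. The four within-group tests are not counted in them. The matter should be fixed, because the remedy is cheap and the primary conclusion depends on it. It does not invalidate the design.

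**What to change.** Replace the single threshold sentence with a rule for the primary objective, for example:

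*The between-arm comparisons of muscle strength and muscle mass are the only primary tests. They are controlled by the Holm procedure at a two-sided family-wise level of 0.05: the smaller p-value is compared with 0.025 and, if significant, the larger with 0.05. All within-group tests and all other outcomes are secondary or exploratory.*

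If a record dated before data lock shows that both outcomes were meant to be required, state instead that benefit is claimed only if both between-arm tests have p below 0.05 in favour of vitamin D. Study Dates gives "Start: November 2023 End of follow-up/data lock: April 2024", so any rule adopted after that lock should be reported as post hoc; it does not restore prespecification.

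If the power statement is revised, give it under the chosen rule and name the outcome. An unadjusted per-outcome figure would describe neither rule.

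**Cost.** A change of wording and no extra participants. Under Holm at 1.1 SD, power per outcome falls from about 80% to about 70% if only one outcome has an effect, and to about 75–77% if both do. In the latter case the chance of at least one significant result falls from 87–96% to 80–91%. Under the both-required rule, power at 1.1 SD in both outcomes is about 63–72%. If only one outcome has an effect, the claim is made at most about 2.3% of the time, because the other must be significant in favour of vitamin D by chance.
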